6.4 Safety

Safety parameters include the following: deaths; AEs; laboratory tests; vital signs; physical measurements; electrocardiograms (ECGs); and C-SSRS.

Measurements are slotted into analysis periods and analysis visits using the following steps:

- 1) Measurements are slotted into the pretreatment, on-treatment safety and follow-up safety analysis periods.
- 2) Measurements are slotted into analysis visits in the analysis periods listed in the previous step. This does not apply to AEs.

Refer also to the Core SAP for details about measurement slotting. See Sections [6.2.5](#), [7.2](#), and [7.3](#) for definitions of baseline, analysis periods, and analysis visit windows, respectively.

6.4.1 Adverse Events

Refer to the Core SAP for the following: AE start and end date imputation; death date derivation; counting and rounding rules in AE frequency tables; definitions of AEs related to study drug, AEs of special interest, and exposure-adjusted multiple occurrences of unique AEs; and TLF contents.

Frequency tables of AEs by SOC and PT display AEs in descending order of overall frequency within SOC and PT, unless otherwise specified.

The by-subject listing of AEs (i.e., non-SAEs and SAEs) is provided for the enrolled analysis set.

6.4.1.1 Deaths

Deaths are identified from any the following sources:

- AE CRF with any of the following: PT or reported term of “death”; outcome of “fatal”; “yes” response to any death-related question (e.g., “Did the AE result in death?”; “Is a death certificate available?”; “Is an autopsy report available?”); complete or partially complete death date.
- Treatment Phase Subject Status CRF with any of the following: death as reason for OLT Phase noncompletion; death as reason for not continuing to the Follow-Up Phase.
- Follow-Up Subject Status CRF: death as reason for Follow-Up Phase noncompletion.

The by-subject listing of deaths is provided for the enrolled analysis set.

6.4.1.2 AE Overview

The AE overview frequency table displays the following categories without SOC and PT: any AE; AE related to study drug; AE leading to study drug discontinuation; SAE; SAE related to study drug; medication-overuse headache AE; hepatic-related AE; hepatic-related AE leading to study drug discontinuation; potential drug abuse AE; cardiovascular AE; and suicidality AE.

AE overview frequency tables are provided for the following analysis periods and analysis sets:

- On-treatment AEs for the safety analysis set
- Follow-up AEs for the follow-up safety analysis set.

6.4.1.3 *On-Treatment AEs*

Frequency tables of on-treatment AEs are provided for the safety analysis set by SOC and PT for the following endpoints:

- AEs by worst intensity
- AEs occurring with $\geq 5\%$ frequency by worst intensity (supports the primary objective). The 5% cut applies only to total intensity.
- AEs related to study drug by worst intensity
- SAEs (supports the primary objective)
- AEs leading to study drug discontinuation (supports the primary objective)
- Potential drug abuse AEs, displayed in alphabetical order by worst intensity and PT without SOC (supports the exploratory objective #1)
- Hepatic-related AEs by intensity (supports exploratory objective #2)
- Hepatic-related AEs leading to study drug discontinuation
- Cardiovascular AEs
- Suicidality AEs.

Calculations for on-treatment exposure-adjusted multiple occurrences of unique AEs use an analysis period reference start date = study drug start date, analysis period reference end date = study drug last date + 7 days if the study drug last date is nonmissing, and analysis period reference end date = study drug end date if the study drug last date is missing.

6.4.1.4 *Follow-Up AEs*

Frequency tables of follow-up AEs are provided by SOC and PT for the follow-up safety analysis set for the following endpoints:

- AEs by worst intensity
- SAEs.

6.4.2 *Laboratory Tests*

Laboratory tests are analyzed using results from local laboratory tests reported on CRFs and the external central laboratory ACM Global Laboratories. The central laboratory reports both laboratory collection date and time, whereas CRFs capture only laboratory collection date. TLFs display results in both Systeme Internationale (SI) and United States (US) units, if applicable.

Laboratory tests of clinical interest are collected at the following visits:

- Hematology: Screening; Weeks 2, 4, 8, 12, 16, 24, and EOT.
- Serum chemistry (including LFTs and lipids): Screening; Weeks 2, 4, 8, 12, 16, 24, and EOT. Exceptions are for the following:
 - LFTs (ALT, AST, ALP, TBL, direct bilirubin, indirect bilirubin): all visits during the study.
 - Lipids (total cholesterol, high-density lipoprotein [HDL] cholesterol, low-density lipoprotein [LDL] cholesterol, triglycerides): Screening; Week 12, Week 24, and EOT.
- Urinalysis: Screening; Week 24 and EOT.

The following by-subject laboratory test listings are provided for the enrolled analysis set:

- Laboratory test results using the Common Technical Criteria for Adverse Events/Division of Acquired Immune Deficiency Syndrome (CTCAE/DAIDS) toxicity grading scale (SI units). The listing displays all test results over time for subjects with grade 3 to 4 laboratory test abnormalities at any time point.
- Laboratory test results using the Food and Drug Administration (FDA) toxicity grading scale (US units). The listing displays all test results over time for subjects with grade 3 to 4 laboratory test abnormalities at any time point.
- LFT values and ratios to ULN (i.e., ALT, AST, TBL and ALP) for SI and US units. The listing displays all LFT results over time for subjects with select LFT elevations (ALT or AST > 3x ULN; ALP or TBL > 2x ULN) at any time point.
- Pregnancy test results. The listing displays all pregnancy test results over time for subjects with a positive pregnancy test at any time point.

Refer to the protocol for laboratory tests of clinical interest. Refer to the Core SAP for toxicity grades and TLF contents.

6.4.2.1 *Laboratory Test Abnormalities*

Frequency tables of worst (highest) laboratory test abnormalities for each graded laboratory test are provided for the following safety analysis periods and analysis sets:

- On-treatment for the safety analysis set
- Follow-up for the follow-up analysis set.

Grade 3 to 4 results support the primary objective.

The frequency table of laboratory test shift from baseline to the worst abnormality on treatment for each graded laboratory test is provided for the safety analysis set.

Separate tables are provided for each toxicity grading scale: CTCAE/DAIDS using SI units; and FDA using US units.

6.4.2.2 Liver Function Test Elevations

Analyses use SI units. Refer to the Core SAP for additional details.

LFT Elevations

Frequency tables of LFT elevations are provided for the following analysis periods and analysis sets:

- On-treatment for the safety analysis set (supports exploratory objectives #3, 4, and 5)
- Follow-up for the follow-up safety analysis set.

Note that in the analysis of ALT or AST $> 3x$ ULN concurrent with a select AE, the AE PT of “anorexia” specified in the Core SAP is replaced with the PT of “decreased appetite” because “anorexia” is no longer in MedDRA.

LFT Shifts From Baseline to Worst Elevation

The frequency table of LFT shift from baseline to the worst (highest) on-treatment LFT elevation is provided for the safety analysis set.

Time to LFT Elevations

The frequency table of time to first on-treatment LFT elevations (ALT $> 3x$ ULN; AST $> 3x$ ULN; ALT or AST $> 3x$ ULN) is provided for subjects in the safety analysis set with on-treatment LFT elevations in the following categories: ≤ 2 , > 2 to ≤ 4 , > 4 to ≤ 8 , ..., > 24 weeks. Time to elevation is calculated as (LFT collection date – study drug start date + 1)/7.

LFT Plots

The on-treatment evaluation of drug-induced serious hepatotoxicity (eDISH) scatter plot is provided for the safety analysis set with paired ALT and TBL ratios on treatment.

By-subject line LFT plots are provided for the safety analysis set with select LFT elevations in any analysis period. Study weeks are defined as study day/7, where study day is derived from the laboratory test collection date (see Section 7.3). Each figure also displays study drug dosing days using symbols along the x-axis (see Section 9.2), and additional study milestones (e.g., start of the on-treatment safety analysis period, and start of the follow-up safety analysis period) using vertical lines with their corresponding descriptions in footnotes.

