Subjects will continue to record all concomitant medications, including standard of care migraine medications (both prophylactic and acute, prescribed and OTC), taken during the entire Follow-up Phase in a concomitant medication paper diary.

4.3.3.1 *Follow-up Week 2 Visit*

Subjects will return to the study site approximately 2 weeks (14 days +/- 2 days) after the Week 24 or EOT Visit to collect vital signs, LFTs, assessment of AEs/SAEs, to have the C-SSRS performed, and to have a urine pregnancy test performed (WOCBP).

Investigators should assess subjects for AEs consistent with drug dependency or withdrawal effects and report as appropriate (see [Section 7.4](#)).

4.3.3.2 *Follow-up Week 8 Visit*

Subjects will return to the study site approximately 8 weeks (56 days +/- 2 days) after the Week 24 or EOT Visit to collect vital signs, LFTs, assessment of AE/SAEs, and to have a serum pregnancy test performed (WOCBP). Subjects will return the concomitant medication paper diary for documenting concomitant medications.

The visit window for the Follow-up Week 8 Visit is 56 days +/- 2 days; however, in cases of a delayed visit due to restrictions resulting from the COVID-19 pandemic, + 14 days may be utilized instead of + 2 days in order to ensure this final visit is completed in person.

4.4 *Post Study Access to Therapy (if applicable)*

At the conclusion of this study, subjects or investigators will not have access to the study drug. The investigator should ensure that the subject receives appropriate standard of care to treat the condition under study.

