Process for abnormal liver function tests: If at any visit after initiation of study drug the AST or ALT is $> 3x$ ULN, the following steps should be taken as soon as the investigator is aware: 1. The subject must be informed of the results and instructed to stop study drug, 2. The subject must be instructed to return to the clinic within 3-5 days for Unscheduled visit for repeat LFT panel and further clinical evaluation and testing as appropriate (with consultation with the Medical Monitor, and 3. The Medical Monitor and Pfizer Medical Monitor (if separate) should immediately be contacted. Guidance will be provided to augment management as appropriate.

8.5 Environmental Exposure, Exposure During Pregnancy or Breastfeeding, and Occupational Exposure

Environmental exposure occurs when a person not enrolled in the study as a subject receives

unplanned direct contact with or exposure to the study drug. Such exposure may or may not lead to the occurrence of an AE or SAE. Persons at risk for environmental exposure include healthcare providers, family members, and others who may be exposed. An environmental exposure may include EDP, EDB, and occupational exposure.

Any such exposures to the study drug under study are reportable to Pfizer Safety within 24 hours of investigator awareness.

8.5.1 *Exposure During Pregnancy*

If, following the Baseline Visit it is subsequently discovered that a study subject is pregnant or may have been pregnant at the time of the investigational product exposure, including during at least 6 half-lives after the product administration, the investigational product will be permanently discontinued in an appropriate manner (i.e., dose tapering if necessary for subject safety). Protocol-required procedures for the study discontinued and the follow-up must be performed on the subject unless contraindicated by the pregnancy (i.e., x-ray studies). Other appropriate pregnancy follow-up procedures should be considered if indicated. The investigator must immediately notify the Pfizer (or designee) Medical Monitor and report the event by either using the PSSA tool and by completing an Exposure During Pregnancy (EDP) Supplemental Form following the SAE reporting procedures as described in [Section 8.1.2](#).

Follow-up information regarding the course of the pregnancy, including perinatal and neonatal outcome and, where applicable offspring information must be reported on an EDP Supplemental Form.

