3.2 Estimands

An estimand is the target of estimation to address the scientific question of interest posed by a study objective. The 4 attributes of an estimand include the population of interest, endpoint of interest, summary of the endpoint, and specification of how intercurrent events are reflected in the scientific question of interest.

For all objectives, the population of interest is defined through appropriate inclusion/exclusion criteria to reflect the targeted patient population for approval. Refer to the protocol for inclusion/exclusion criteria.

Intercurrent Events

Intercurrent events are those that occur after treatment initiation and either preclude observation of the endpoint or affect its interpretation. Study drug discontinuation before the time point of interest defining the endpoint is considered an intercurrent event.

For safety objectives, study drug discontinuation is handled with a “while-on-treatment strategy,” i.e., response to treatment prior to the occurrence of the intercurrent event of interest, such that all observed values of the endpoint of interest are used prior to study drug discontinuation plus 7 days (see Section 7.2 and the Core SAP).

Refer to Section 4.1 for analysis sets that are used to assess endpoints.

Data Sources for Endpoints

AEs are determined from AE case report forms (CRFs).

Grade 3 to 4 laboratory test abnormalities are determined from laboratory test values graded using standardized criteria. Laboratory test results are from an external central laboratory and local laboratory test CRFs.

C-SSRS parameters are derived from the C-SSRS CRF.

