3.2.3 Exploratory Objective Estimands

The estimands corresponding to the exploratory objectives are shown in Table 2.

Table 2 Exploratory Objective Estimands

Objective	Frequency of AEs potentially associated with drug abuse during the OLT Phase
Safety Endpoint	Number and percentage of subjects with potential drug abuse AEs on treatment
Summary	Frequency for the safety analysis set
Intercurrent Events	Study drug discontinuation: while-on-treatment strategy
Objective	Frequency and intensity of hepatic-related AEs during the OLT Phase
Safety Endpoint	Number and percentage of subjects with hepatic-related AEs by intensity on treatment
Summary	Frequency for the safety analysis set
Intercurrent Events	Study drug discontinuation: while-on-treatment strategy
Objective	Frequency of LFT elevations based on fold changes above ULN during the OLT Phase
Safety Endpoint	Number and percentage of subjects with LFT elevations (ALT, AST, ALP, or TBL) based on fold changes above ULN on treatment
Summary	Frequency for the safety analysis set with LFT data on treatment
Intercurrent Events	Study drug discontinuation: while-on-treatment strategy
Objective	Frequency of ALT or AST > 3x ULN concurrent with TBL > 2x ULN during the OLT Phase
Safety Endpoint	Number and percentage of subjects with ALT or AST > 3x ULN concurrent with TBL > 2x ULN on treatment
Summary	Frequency for the safety analysis set with LFT data on treatment
Intercurrent Events	Study drug discontinuation: while-on-treatment strategy

Objective	Frequency of ALT or AST > 3x ULN in temporal association with nausea, vomiting, anorexia, abdominal pain, or fatigue during the OLT Phase
Safety Endpoint	Number and percentage of subjects with ALT or AST > 3x ULN concurrent with AEs of nausea, vomiting, anorexia, abdominal pain, or fatigue on treatment
Summary	Frequency for the safety analysis set with LFT data on treatment
Intercurrent Events	Study drug discontinuation: while-on-treatment strategy
Objective	C-SSRS during the OLT Phase
Safety Endpoint	Number and percentage of subjects with any of the following findings on treatment: suicidal ideation; suicidal behavior; suicidal ideation or behavior; and non-suicidal self-injurious behavior.
Summary	Frequency for the safety analysis set with C-SSRS data on treatment
Intercurrent Events	Study drug discontinuation: while-on-treatment strategy

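### The paired ALT/AST and bilirubin count and the eDISH plot end 7 days after last dose, so a bilirubin rise after the protocol's own drug stop can go uncounted; one supplementary row and plot would show it

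*SAP*

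**What the plan says.** **Endpoint.** SAP 3.2.3 defines the endpoint for exploratory objective 4 as "Number and percentage of subjects with ALT or AST > 3x ULN concurrent with TBL > 2x ULN on treatment".

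**Window.** SAP 3.2 handles drug discontinuation with a while-on-treatment strategy, so that "all observed values of the endpoint of interest are used prior to study drug discontinuation plus 7 days". SAP 6.4 adds: "Measurements are slotted into the pretreatment, on-treatment safety and follow-up safety analysis periods". In SAP Table 3 the follow-up windows start at follow-up day 8.

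**Displays.** SAP 6.4.2.2 plans LFT elevation tables separately by period: on treatment for the safety analysis set, and "Follow-up for the follow-up safety analysis set". The eDISH "scatter plot is provided for the safety analysis set with paired ALT and TBL ratios on treatment". No table or eDISH plot combines the two periods.

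**Drug stop and later draws.** Protocol 8.4, for AST or ALT > 3x ULN after drug start: "The subject must be informed of the results and instructed to stop study drug". It continues: "The subject must be instructed to return to the clinic within 3-5 days for Unscheduled visit for repeat LFT panel". Further testing is left to clinical judgement with the medical monitor. The next scheduled LFTs after the EOT Visit are at Follow-up Week 2 (Protocol 4.3.3.1: "Subjects will return to the study site approximately 2 weeks (14 days +/- 2 days) after the Week 24 or EOT Visit") and Follow-up Week 8 (56 +/- 2 days, Protocol 4.3.3.2).

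**The concern.** The two halves of the paired criterion need not cross their thresholds on the same day. Here the first half, ALT or AST > 3x ULN, is also the protocol's trigger for stopping drug, and the stop starts the 7-day clock. A bilirubin rise that comes later is slotted to follow-up. If the transaminases have recovered by then, neither period holds a pair that meets the criterion.

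Any resulting error has one direction: for these subjects the tabulated count can only be too low. The paired count and eDISH are the summary displays a reader would turn to first for serious liver injury in a daily-dosing safety study. The report could also look inconsistent. The potential-DILI definition in Protocol 8.4 sets no 7-day limit, and SAEs are collected through Follow-up Week 8 (Protocol 8.1.2). A potential-DILI SAE could then stand beside a paired count of zero.

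**Working it through.** **1. The plan's own precision figure.** SAP 5 and Protocol 9.1 give 0.01 as the one-sided 95% upper bound for 0 events in 285. The exact value is 1 - 0.05^(1/285) = 0.01046, and the rule of three gives 3/285 = 0.01053. Both round to 0.01, so the figure is reproduced.

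**2. Timeline.** Count days from last dose, with days 0 to 7 on treatment and day 8 onward follow-up. This reads SAP 3.2 with Table 3; the formal boundaries are in the Core SAP.
- Repeat panel at 3-5 days: on treatment, if counted from last dose.
- Follow-up Week 2: at least 14 - 2 = 12 days after the EOT Visit. If that visit is on or after the last dose, the draw is in follow-up.
- Follow-up Week 8: at least 56 - 2 = 54 days after the EOT Visit, so in follow-up.
- The EOT Visit and unscheduled draws can fall on either side of day 7.

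**3. Where a case lands.** Take a subject with on-treatment ALT > 3x ULN, a permanent stop, and pairing by the same draw. The same-draw rule is an assumption, since the SAP leaves the details to the Core SAP.

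| TBL > 2x ULN first drawn | ALT or AST at that draw | Paired row | TBL rise in eDISH |
|---|---|---|---|
| Day 7 or earlier | > 3x ULN | On treatment | Yes |
| Day 8 or later | still > 3x ULN | Follow-up | No |
| Day 8 or later | both <= 3x ULN | Neither | No |

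The third line is the gap. A bilirubin rise by day 7 with ALT already <= 3x ULN depends on how the Core SAP defines concurrent, and is not part of this point.

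**4. Can the third line plausibly occur?** The documents give no rate of ALT decline. Assume ALT(t) = A x 0.5^(t/h), where A is ALT at last dose in multiples of ULN and h is a half-life of 2, 4 or 7 days, with AST no higher than ALT. Time to reach 3x ULN is h x log2(A/3).
- A = 8: ALT reaches 3x ULN after 2.8, 5.7 or 9.9 days. On day 10 it is 0.25x, 1.41x or 2.97x ULN, so a bilirubin rise first seen that day falls in neither row.
- A = 4 to 10, bilirubin rise first seen on day 14: neither row for all three half-lives. The highest ALT is 10 x 0.5^(14/7) = 2.5x ULN.
- A = 10, h = 7, day 10: ALT is 3.71x ULN, so the follow-up row counts the case.
- A = 20, h = 7, day 14: ALT is 5.0x ULN, so the follow-up row counts the case.

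The gap is therefore possible over a broad range but not automatic. None of these day-10 or day-14 bilirubin rises appears in the on-treatment eDISH plot.

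**5. Scale of one case.** With 0/285 the upper bound is 1.05%. One case gives 1/285 = 0.35%, and the exact (Clopper-Pearson) one-sided bound, the 0.95 quantile of Beta(2, 284), is 1.65%. SAP 3.2.3 restricts the denominator to subjects with on-treatment LFT data, so it may be below 285.

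**The case against.** **The case is outside the endpoint.** Objective 4 asks for concurrent elevations during the Open-Label Treatment Phase. A late bilirubin rise after ALT has recovered is neither concurrent nor on treatment, so a reader who infers an error against the stated objective goes too far. This stands, and it is why the remedy is supplementary.

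**The pairing rule may be in the Core SAP.** SAP 6.4.2.2 refers there for details. A cross-period rule would remove the gap in the count, so the point is conditional on that document.

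**Monitoring is more than one repeat panel.** Protocol 8.4 allows further testing, the EOT Visit includes LFTs, and events leading to discontinuation are followed to conclusion or stabilization (Protocol 8.2.1). The 7 days run from discontinuation, which can come after the abnormal draw. If dosing resumes, the study drug end date moves later (SAP 7.1) and the intervening values stay on treatment. All of this narrows the gap to permanent stops with a late bilirubin rise.

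**The subject is not hidden.** The LFT listing (SAP 6.4.2) gives the full LFT course for anyone with a select elevation, and the line plots span all periods. On-treatment ALT or AST > 3x ULN triggers a narrative (SAP 6.4.6). A case meeting the potential-DILI definition is reported as an SAE. This also stands, but these outputs work subject by subject and none supplies the count or the eDISH point.

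**The separate analysis set loses nobody.** The follow-up safety set is defined by last contact date, which includes laboratory dates (SAP 4.1, 7.1). A subject with a follow-up LFT belongs to it.

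**Conclusion.** A cheap improvement, not an error in the stated estimand. On the visible text, a subject with on-treatment ALT or AST > 3x ULN who stops permanently, and whose TBL first exceeds 2x ULN after day 7 with ALT and AST then <= 3x ULN, is in neither paired row, and eDISH does not show the bilirubin rise. The ALT or AST elevation remains in the on-treatment table and the bilirubin elevation can appear in the follow-up table; what is lost is the link between them.

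This assumes that the Core SAP does not pair across periods and that days are counted from last dose. The number of such subjects cannot be derived from the documents and may be zero.

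A reader might infer that one missed case overturns the plan's claim to rule out rates above 1 in 100. The documents do not support that. The statement is a general sample-size rationale, no interval or rule-out is planned for objective 4, and 0/285 already gives 1.046%. The move from 1.05% to 1.65% shows scale only.

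**What to change.** Keep the while-on-treatment estimand and all planned tables. Add to SAP 6.4.2.2:

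1. **One supplementary row** for the safety analysis set: on-treatment ALT or AST > 3x ULN with TBL > 2x ULN on or after that date and within a pre-stated pairing window. One example is through the end of the Follow-Up Week 2 analysis window, follow-up day 35 (SAP Table 3). Without a limit, a Week 2 ALT could be paired with a bilirubin value at Follow-up Week 8 after a Week 24 Visit, 24 + 8 - 2 = 30 weeks later. Mark subjects who resumed dosing after the elevation, because a limit set in follow-up days does not bound their interval.
2. **One supplementary eDISH plot** of peak ALT and peak TBL over on-treatment plus follow-up values.
3. **Flags in both** for components dated after last dose + 7 days, elevated baseline TBL (including Gilbert's syndrome, for which Protocol 5.3 has its own bilirubin provision) and elevated ALP.

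Also state the pairing rule for concurrent elevations in the study SAP. If the Core SAP already pairs across periods, that statement settles the count.

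Cost: one row and one plot from LFTs already scheduled at every visit, with no change to visits or study drug handling. Some late bilirubin rises will be unrelated to drug, so both versions should be shown.
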